7.8. Treatment after the End of the Study

7.8.1. Treatment after Study Completion

Tirzepatide will not be made available after conclusion of the study to patients.

7.8.2. Special Treatment Considerations

Investigators will be trained on how to apply decision criteria for the timing and method of intervention in patients who do not reach glycemic targets during the treatment period. An additional therapeutic intervention should be considered for patients with persistent hyperglycemia as described in Section [9.2.2.2](#).

8. Discontinuation Criteria

8.1. Discontinuation from Study Treatment

8.1.1. *Permanent Discontinuation from Study Treatment*

Possible reasons leading to permanent discontinuation of investigational product:

- **Patient Decision**
 - The patient requests to discontinue investigational product.
- **Discontinuation due to a hepatic event or liver test abnormality.** Patients who are discontinued from investigational product due to a hepatic event or liver test abnormality should have additional hepatic safety data collected via the electronic case report form (eCRF).

Discontinuation of the investigational product for abnormal liver tests **should be** considered by the investigator when a patient meets one of the following conditions after consultation with the Lilly designated medical monitor:

- ALT or aspartate aminotransferase (AST) >8X ULN
- ALT or AST >5X ULN for more than 2 weeks
- ALT or AST >3X ULN and total bilirubin level (TBL) >2X ULN or international normalized ratio (INR) >1.5
- ALT or AST >3X ULN with the appearance of fatigue, nausea, vomiting, right upper-quadrant pain or tenderness, fever, rash, and/or eosinophilia (>5%)
- alkaline phosphatase (ALP) >3X ULN
- ALP >2.5X ULN and TBL >2X ULN
- ALP >2.5X ULN with the appearance of fatigue, nausea, vomiting, right quadrant pain or tenderness, fever, rash, and/or eosinophilia (>5%)

In addition, patients will be discontinued from the investigational product in the following circumstances:

- If a patient is inadvertently enrolled and it is determined that continued treatment with study drug would not be medically appropriate, see Section [8.1.3](#)
- Acute or chronic pancreatitis
- If a patient is diagnosed with MTC after randomization, or has a postrandomization calcitonin value ≥ 35 ng/mL that has increased at least 50% over baseline
- If a patient is diagnosed with an active or untreated malignancy (other than basal or squamous cell skin cancer, in situ carcinomas of the cervix, or in situ prostate cancer) after randomization
- Any significant study drug-related hypersensitivity reaction

- Any other TEAE, SAE, or clinically significant laboratory value for which the investigator believes that permanent study drug discontinuation is the appropriate measure to be taken
- If female patient becomes pregnant
- If a patient is diagnosed with T1DM

Patients who stop the study drug permanently will receive another glucose-lowering intervention (Section 7.4.2) and will continue participating in the trial according to the protocol to collect all planned efficacy and safety measurements.

Patients discontinuing from the investigational product prematurely for any reason should complete AE and other follow-up procedures per Section 2 Schedule of Activities, Section 9.2 Adverse Event, and Section 9.4 Safety of this protocol.

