- ^p Follicle-stimulating hormone test performed at Visit 1 for potential postmenopausal women age 45 years or above with an intact uterus, not on hormone therapy or oral contraceptives, and who have had spontaneous amenorrhea for more than 6 months and less than 12 months and estradiol levels consistent with a postmenopausal state (FSH \geq 40 mIU/mL and estradiol <30 pg/mL).
- ^q Screening visit assessment will serve as baseline.
- ^r The CKD-EPI equation will be used by the central lab to estimate and report eGFR.
- ^s In the event of systemic drug hypersensitivity reactions (immediate or nonimmediate), additional blood samples will be collected including ADA, PK, and an exploratory immune safety sample.
- ^t PK samples for immunogenicity must be taken prior to drug administration.
- ^u All PROs should be completed before any other study procedures if the patient is not adversely affected by the fasting condition or completed after the patient has sufficiently recovered from the preceding visit procedures.

Note: Patients will be encouraged to collect a daily fasting BG and a weekly 4-point SMBG. Missing a fasting BG measurement will not be considered a protocol deviation.

3. Introduction

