- [21] Have family or personal history of medullary thyroid carcinoma (MTC) or multiple endocrine neoplasia syndrome type 2 (MEN-2)

- [22] Have a serum calcitonin level of ≥ 35 ng/L (pg/mL), as determined by central laboratory at Visit 1
- [23] Known or suspected hypersensitivity to trial product(s) or related products
- [24] Have evidence of a significant, active autoimmune abnormality (for example, lupus or rheumatoid arthritis) that, in the opinion of the investigator, is likely to require concurrent treatment with systemic glucocorticoids in the next 12 months
- [25] Have had a transplanted organ (corneal transplants [keratoplasty] allowed) or awaiting an organ transplant
- [26] Have a history of an active or untreated malignancy, or are in remission from a clinically significant malignancy (other than basal or squamous cell skin cancer, in situ carcinomas of the cervix, or in situ prostate cancer) for less than 5 years
- [27] Have a history of any other condition (such as known drug or alcohol abuse or psychiatric disorder) that, in the opinion of the investigator, may preclude the patient from following and completing the protocol
- [28] Have any hematological condition that may interfere with HbA1c measurement (for example, hemolytic anemias, sickle-cell disease)

Prior/Concomitant Therapy

- [29] Treatment with any glucose lowering agent(s) other than stated in the inclusion criteria # 2 in a period of 2 months prior to Visit 1 and between Visit 1 and Visit 3
- [30] Have been treated with prescription drugs that promote weight loss (e.g., Saxenda (liraglutide 3.0 mg), Xenical® [orlistat], Meridia® [sibutramine], Acutrim® [phenylpropanolamine], Sanorex® [mazindol], Apidex® [phentermine], BELVIQ® [lorcaserin], Qsymia™ [phentermine/topiramate combination], contrave® [naltrexone/bupropion] or similar other body weight loss medications including over-the-counter [OTC] medications [e.g., alli®]) within 3 months prior to Visit 1 and/or between study entry (Visit 1) and randomization (Visit 3)
- [31] Are receiving chronic (>2 weeks or 14 days) systemic glucocorticoid therapy (excluding topical, intra-ocular, intranasal, or inhaled preparations) or have received such therapy within 1 month of Visit 1; or between Visits 1 and 3

Prior/Concurrent Clinical Trial Experience

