9.2.2.4. Thyroid Malignancies and C-Cell Hyperplasia

Individuals with personal or family history of MTC and/or MEN-2 will be excluded from the study. The assessment of thyroid safety during the trial will include reporting of any case of thyroid malignancy including MTC and papillary carcinoma and measurements of calcitonin. This data will be captured in specific eCRFs. The purpose of calcitonin measurements is to assess the potential of tirzepatide to affect thyroid C-cell function, which may indicate development of C-cell hyperplasia and neoplasms. Tirzepatide should be discontinued (after first confirming the value) if post randomization calcitonin value is ≥ 35 ng/L (pg/mL) and has increased at least 50% over baseline. A consultation with a thyroid specialist (if not available, an endocrinologist) should be obtained.

If the increased calcitonin value (≥ 35 pg/mL and increases by $\geq 50\%$ compared to baseline) is observed in a patient who has administered a medication that is known to increase serum calcitonin, this medication should be stopped and calcitonin levels should be measured after an appropriate wash out period. If the confirmed calcitonin value is < 35 pg/mL, tirzepatide should be restarted when it is safe to do so.

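### The calcitonin threshold for permanently stopping study drug in Protocol 8.1.1 is in ng/mL, 1000 times the ng/L (pg/mL) threshold that 9.2.2.4 gives for the same rule

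*Protocol*

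**What the plan says.** Protocol 8.1.1 introduces its list in mandatory terms: "patients will be discontinued from the investigational product in the following circumstances". The thyroid item covers a diagnosis of medullary thyroid carcinoma (MTC) or a post-randomization calcitonin of at least "35 ng/mL that has increased at least 50% over baseline". It has no confirmation step and no reference to the thyroid section. Another item in the same list, on inadvertent enrolment, does refer the reader onward (to 8.1.3).

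Protocol 9.2.2.4, the thyroid safety section, gives the rule again: "Tirzepatide should be discontinued (after first confirming the value) if post randomization calcitonin value is" at least "35 ng/L (pg/mL) and has increased at least 50% over baseline". It returns to pg/mL for patients on a drug known to raise calcitonin. For them, after washout, if the confirmed value is below "35 pg/mL, tirzepatide should be restarted when it is safe to do so".

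Two other places set calcitonin limits:

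- Exclusion criterion 22 (Protocol 6.2) excludes patients at or above "35 ng/L (pg/mL), as determined by central laboratory at Visit 1".
- SAP 6.13.2.4.1 reports calcitonin in ng/L, with a top category above 100 ng/L.

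For the calcitonin row of the Schedule of Activities, footnote q says "Screening visit assessment will serve as baseline".

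**The concern.** Sections 8.1.1 and 9.2.2.4 describe one rule, with the same number, the same 50% rise and the same timing, but in units 1000-fold apart. Only 8.1.1 uses ng/mL. The text is current, and the Amendment (a) summary in Appendix 8 lists no change to it.

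The error sits in a stopping rule, and in the more strongly worded of the two statements: 8.1.1 says that drug will be stopped, while 9.2.2.4 says that it should be. Taken literally, the calcitonin limb of 8.1.1 could not work as a check for C-cell effects.

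Scheduled testing is sparse: Weeks 12, 24 and 40 on treatment, plus early termination and follow-up. If a trigger at Week 12 were missed, the next scheduled test is at Week 24. By then a patient in the 15 mg group who followed the escalation schedule would be at full dose. Serum calcitonin is also a named safety endpoint.

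**Working it through.** **Inputs**

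| Input | Value | Source |
|---|---|---|
| Stopping threshold, list of mandatory reasons | ≥35 ng/mL and ≥50% rise | Protocol 8.1.1 |
| Stopping threshold, thyroid section | ≥35 ng/L (pg/mL) and ≥50% rise | Protocol 9.2.2.4 |
| Entry limit | excluded if ≥35 ng/L (pg/mL) at Visit 1 | Protocol 6.2, criterion 22 |
| Baseline calcitonin, *b* | screening value, so *b* < 35 ng/L | Schedule of Activities, footnote q, with criterion 22 |
| Start of top reporting category | 100 ng/L | SAP 6.13.2.4.1 |

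**Step 1: common units.** 1 ng/mL = 1000 ng/L, and 1 ng/L = 1 pg/mL.

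- 8.1.1: 35 × 1000 = 35,000 ng/L.
- 9.2.2.4: 35 ng/L = 35 / 1000 = 0.035 ng/mL.
- Ratio: 35,000 / 35 = 1000.
- Against the SAP's top category: 35,000 / 100 = 350 times the value at which it starts.

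**Step 2: effective trigger with both conditions.** A patient must reach the threshold and also rise by at least 50%, so the trigger is max(threshold, 1.5*b*).

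- Under 9.2.2.4 it is max(35, 1.5*b*). The 50% condition takes over when *b* > 35 / 1.5 = 23.3 ng/L. The trigger is therefore 35 ng/L for *b* up to 23.3, rising to just under 1.5 × 35 = 52.5 ng/L as *b* approaches 35.
- Under 8.1.1 it is max(35,000, 1.5*b*), which is 35,000 ng/L for every *b* below 35.
- Ratio of effective triggers: from 35,000 / 52.5 = 667 to 35,000 / 35 = 1000, depending on baseline.

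**Step 3: does the 8.1.1 rule make sense on its own terms?**

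- The 50% condition would matter only if *b* > 35,000 / 1.5 = 23,333 ng/L. That is 23,333 / 35 = 667 times the entry limit, so no eligible patient can be affected by it.
- The smallest rise that meets 8.1.1 exceeds 35,000 / 35 = 1000-fold.
- In ng/L, the 50% condition does real work for baselines between 23.3 and 35 ng/L. Only that unit makes the two-part rule coherent.

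**Step 4: the gap between the sections.** A confirmed value from 35 ng/L to just below 35,000 ng/L, with a rise of at least 50%, calls for stopping tirzepatide under 9.2.2.4 but does not meet the calcitonin limb of 8.1.1.

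**The case against.** The best defence is that the protocol read as a whole still stops the drug. Any value that meets 8.1.1 literally also meets the threshold in 9.2.2.4, and nothing in 8.1.1 tells a site to continue below its own limit. A tirzepatide patient with a confirmed 40 ng/L and the required rise is covered by 9.2.2.4. Section 8.1.1 also stops drug for diagnosed MTC, and for any "clinically significant laboratory value for which the investigator believes that permanent study drug discontinuation is the appropriate measure". The figure of 35,000 ng/L is so implausible that a careful investigator would probably see the slip. Nothing shows that sites would read 8.1.1 in preference to 9.2.2.4. All of this stands, and it limits the practical risk. It does not make the 8.1.1 threshold correct.

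A second point concerns baseline. SAP 6.2 takes the latest value between Visits 1 and 3, unscheduled visits included, whereas criterion 22 limits only the Visit 1 value. The 52.5 ng/L ceiling is therefore not strictly guaranteed under the SAP definition. This has little force, because Visit 1 is the only scheduled calcitonin test before dosing, and the factor of 1000 between the stated thresholds does not depend on baseline at all.

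A third is that the printed unit may have been garbled in transcription. Nothing supports this: the unit in 8.1.1 is complete and legible, and ng/L appears intact everywhere else. A look at the sponsor's source file would settle it.

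Finally, 9.2.2.4 applies to tirzepatide and allows restart in some cases, while 8.1.1 covers the investigational product and is permanent. Changing the unit is the essential correction. Adding confirmation and a cross-reference aligns the two sections and should be worded with that difference in mind.

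**Conclusion.** The point holds. The calcitonin threshold in 8.1.1 is wrong as written: 35,000 ng/L where the rest of the protocol and the SAP point to 35 ng/L, a factor of 1000. With the 50% condition included, the effective trigger is 667 to 1000 times too high. That range assumes that baseline is the screening value and lies below 35 ng/L; the factor of 1000 needs no such assumption.

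This should be fixed, because it is a decision threshold in a mandatory safety rule. The likely harm is small given 9.2.2.4 and the other stopping reasons in 8.1.1. No sample size, power, alpha or efficacy analysis is touched.

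**What to change.** In Protocol 8.1.1, replace the calcitonin condition with: ≥35 ng/L (pg/mL), confirmed, with an increase of at least 50% over baseline (see Section 9.2.2.4).

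The unit is the necessary change. The confirmation step and the reference bring 8.1.1 into line with 9.2.2.4 and lead the reader to its washout and restart provisions.

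The cost is one line in the protocol, or a clarification letter to sites if an amendment is not otherwise planned. Data collection and the SAP analyses stay as they are.

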8.1.2. Temporary Discontinuation from Study Treatment

In certain situations after randomization, the investigator may need to temporarily interrupt study drug. Every effort should be made by the investigator to maintain patients on study drug and to restart study drug after any temporary interruption, as soon as it is safe to do so.

- If the number of doses missed is equal or less than 2, the treatment can be restarted at the same dose, if the drug was well tolerated prior to discontinuation.
- If the number of missed doses is equal or greater than 3, then the treatment should be restarted at 5 mg irrespective of the dose the patient was receiving before the interruption and subsequently escalated as required by protocol.

If study drug interruption is due to an AE, the event is to be documented and followed according to the procedures in Section 9.2 of this protocol. If the study drug interruption is due to intolerable persistent GI AE (for example, nausea, vomiting, or diarrhea), the patients should be treated as suggested in Section 7.7.1. Investigators should inform the sponsor that study drug has been temporarily interrupted.

The data related to temporary interruption of study treatment will be documented in source documents and entered on the eCRF.

8.1.3. Discontinuation of Inadvertently Enrolled Patients

If the sponsor or investigator identify a patient who did not meet enrollment criteria and was inadvertently enrolled, then the patient should be discontinued from study treatment unless there are extenuating circumstances that make it medically necessary for the patient to continue on study treatment. If the investigator and the sponsor CRP agree it is medically appropriate to continue, the investigator must obtain documented approval from the sponsor CRP to allow the inadvertently enrolled patient to continue in the study with or without treatment with investigational product. Safety follow up is as outlined in Section 2 (Schedule of Activities), Section 9.2 (Adverse Events), and Section 9.4 (Safety) of the protocol.

8.2. Discontinuation from the Study

In order to minimize the amount of missing data and to enable assessment of study objectives as planned in the study protocol, every attempt will be made to keep patients in the study irrespective of the following:

- adherence to study drug
- adherence to visit schedule
- missing assessments
- study drug discontinuation due to AE
- development of comorbidities
- development of clinical outcomes

The circumstances listed above are not valid reasons for discontinuation from the study.

Patients will be discontinued in the following circumstances:

- enrollment in any other clinical study involving an investigational product or enrollment in any other type of medical research judged not to be scientifically or medically compatible with this study
- participation in the study needs to be stopped for medical, safety, regulatory, or other reasons consistent with applicable laws, regulations, and good clinical practice (GCP)
- If a female patient becomes pregnant
- If a patient is diagnosed with T1DM
- patient decision requests to be withdrawn from the study

Patients who agree to provide information relevant to any trial endpoint at the end of the study are not considered to have discontinued from the study.

A patient who withdraws consent and clearly indicates that there will be no further contact of any kind with the site will be considered to have discontinued from the study.

Prior to early study discontinuation, the patient will discontinue study drug and will have end-of-study procedures (ET visit) performed as shown in the Schedule of Activities (Section 2).

During the ET visit, the patient will be prescribed an appropriate glucose-lowering regimen and glucose self-monitoring plan. Visit 801 (safety follow-up visit) should be performed approximately 4 weeks after the ET visit as the final study visit.

Patients discontinuing from the study prematurely for any reason should complete adverse event and other safety follow-up per Section 2 (Schedule of Activities), Section 9.2 (Adverse Events), and Section 9.4 (Safety) of this protocol.

8.3. Lost to Follow-Up

A patient will be considered lost to follow-up if he or she repeatedly fails to return for scheduled visits and is unable to be contacted by the study site. Every attempt will be made to minimize the

number of patients considered lost to follow-up at the end of the study. Patients will be informed about the importance of completing the study and providing updated contact information to the study site when necessary.

9. Study Assessments and Procedures

Section 2 lists the Schedule of Activities, with the study procedures and their timing (including tolerance limits for timing).

Appendix 2 lists the laboratory tests that will be performed for this study.

Unless otherwise stated in the subsections below, all samples collected for specified laboratory tests will be destroyed within 60 days of receipt of confirmed test results.

9.1. Efficacy Assessments

9.1.1. Primary Efficacy Assessments and Procedures

The primary efficacy measurement in this study is mean change in HbA1c from baseline to 40 weeks, as determined by the central laboratory. Blood samples for HbA1c measurements will be collected at specific clinic visits as summarized in the Study Schedule, Section 2.

9.1.2. Secondary Efficacy Assessments and Procedures

The following secondary efficacy measures will be assessed at 40 weeks based on data collected at the times shown in the Study Schedule.

- Change in HbA1c from baseline
- Change in weight from baseline
- Proportion of patients achieving a target HbA1c <7% (53 mmol/mol)
- Change in fasting serum glucose from baseline measured in the central laboratory
- Proportion of patients achieving an HbA1c target values of $\leq 6.5\%$ (48 mmol/mol) and $< 5.7\%$ (39 mmol/mol)
- Change in 7-point self-monitored blood glucose (SMBG) profiles
- Proportion of patients who achieved weight loss $\geq 5\%$, $\geq 10\%$, and $\geq 15\%$ from baseline
- Patient-reported outcomes:
 - Diabetes Treatment Satisfaction Questionnaire status and Diabetes Treatment Satisfaction Questionnaire change

9.1.3. Exploratory Efficacy Assessments and Procedures

The following efficacy measures will be calculated based on data collected at the times shown in the Study Schedule.

- Change in lipids (total cholesterol, HDL, VLDL, and TG)
- Change in waist circumference
- Change from baseline in mean BMI
- European Quality of Life dimensions (EQ-5D-5L) scores
- Impact of Weight on Self Perception
- Ability to Perform Physical Activities of Daily Living

9.1.4. Appropriateness of Assessments

Efficacy and safety assessments included in this study are generally regarded as reliable and accurate with respect to the efficacy and safety assessments in individuals and populations with T2DM.

9.2. Adverse Events

Investigators are responsible for monitoring the safety of patients who have entered this study and for alerting Lilly or its designee to any event that seems unusual, even if this event may be considered an unanticipated benefit to the patient.

The investigator is responsible for the appropriate medical care of patients during the study.

Investigators must document their review of each laboratory safety report.

The investigator remains responsible for following, through an appropriate health care option, AEs that are serious or otherwise medically important, considered related to the investigational product or the study, or that caused the patient to discontinue the investigational product (tirzepatide) before completing the study. The patient should be followed until the event resolves, stabilizes with appropriate diagnostic evaluation, or is reasonably explained. For events that are not anticipated to resolve or stabilize, the patient should be followed until the treating physician (in consultation with the sponsor) determines that appropriate follow-up has been completed. The frequency of follow-up evaluations of the AE is left to the discretion of the investigator.

Lack of drug effect is not an AE in clinical studies, because the purpose of the clinical study is to establish treatment effect.

After the informed consent form (ICF) is signed, study site personnel will record via the electronic case report form (eCRF) the occurrence of each patient's preexisting conditions, including clinically significant signs and symptoms of the disease under treatment in the study. In addition, site personnel will record any change in the condition(s) and any new conditions as AEs. For each AE, the onset and duration, the seriousness and severity, and the actions taken with respect to study treatment will be recorded. Investigators should record their assessment of the potential relatedness of each AE to protocol procedure, investigational product, via eCRF.

The investigator will interpret and document whether or not an AE has a reasonable possibility of being related to study treatment, study device, or a study procedure, taking into account the disease, concomitant treatment or pathologies.

A "reasonable possibility" means that there is a cause and effect relationship between the investigational product, study device and/or study procedure and the AE.

The investigator answers yes/no when making this assessment.

Planned surgeries and nonsurgical interventions should not be reported as AEs unless the underlying medical condition has worsened during the course of the study.

If a patient's investigational product is discontinued as a result of an AE, study site personnel must report this to Lilly or its designee via eCRF, clarifying if possible, the circumstances leading to any dosage modifications, or discontinuations of treatment.

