9.2.1. Serious Adverse Events

An SAE is any AE from this study that results in one of the following outcomes:

- death
- initial or prolonged inpatient hospitalization
- a life-threatening experience (that is, immediate risk of dying)
- persistent or significant disability/incapacity
- congenital anomaly/birth defect
- important medical events that may not be immediately life-threatening or result in death or hospitalization but may jeopardize the patient or may require intervention to prevent one of the other outcomes listed in the definition above. Examples of such medical events include allergic bronchospasm requiring intensive treatment in an emergency room or at home, blood dyscrasias or convulsions that do not result in inpatient hospitalization, or the development of drug dependency or drug abuse.

All AEs occurring after signing the ICF are recorded in the eCRF and assessed for serious criteria. The SAE reporting to the sponsor begins after the patient has signed the ICF and has received investigational product. However, if an SAE occurs after signing the ICF, but prior to receiving investigational product, the SAE should be reported to the sponsor as per SAE reporting requirements and timelines (see Section 9.2) if it is considered reasonably possibly related to study procedure.

Study site personnel must alert Lilly or its designee of any SAE within 24 hours of investigator awareness of the event via a sponsor-approved method. If alerts are issued via telephone, they are to be immediately followed with official notification on study-specific SAE forms. This 24-hour notification requirement refers to the initial SAE information and all follow-up SAE information. Patients with a serious hepatic adverse event should have additional data collected using the eCRF.

Pregnancy (during maternal or paternal exposure to investigational product) does not meet the definition of an AE. However, to fulfill regulatory requirements any pregnancy should be reported following the SAE process to collect data on the outcome for both mother and fetus.

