Appendix 1. Abbreviations and Definitions

Term	Definition
AE	adverse event: Any untoward medical occurrence in a patient or clinical investigation subject administered a pharmaceutical product that does not necessarily have a causal relationship with this treatment. An adverse event can therefore be any unfavorable and unintended sign (including an abnormal laboratory finding), symptom, or disease temporally associated with the use of a medicinal (investigational) product, whether or not related to the medicinal (investigational) product.
ALT	alanine aminotransferase
AST	aspartate aminotransferase
CIOMS	Council for International Organizations of Medical Sciences
complaint	A complaint is any written, electronic, or oral communication that alleges deficiencies related to the identity, quality, purity, durability, reliability, safety or effectiveness, or performance of a drug or drug delivery system.
compliance	Adherence to all study-related, good clinical practice (GCP), and applicable regulatory requirements.
CRP	clinical research physician: Individual responsible for the medical conduct of the study. Responsibilities of the CRP may be performed by a physician, clinical research scientist, global safety physician or other medical officer.
ECG	electrocardiogram
enroll	The act of assigning a patient to a treatment. Patients who are enrolled in the study are those who have been assigned to a treatment.
enter	Patients entered into a study are those who sign the informed consent form directly or through their legally acceptable representatives.
GCP	good clinical practice
IB	Investigator's Brochure
ICF	informed consent form
ICH	International Council for Harmonisation
Informed consent	A process by which a patient voluntarily confirms his or her willingness to participate in a particular study, after having been informed of all aspects of the study that are relevant to the patient's decision to participate. Informed consent is documented by means of a written, signed and dated informed consent form.

investigational product	A pharmaceutical form of an active ingredient or placebo being tested or used as a reference in a clinical trial, including products already on the market when used or assembled (formulated or packaged) in a way different from the authorized form, or marketed products used for an unauthorized indication, or marketed products used to gain further information about the authorized form.

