6.13.1. Adverse Events

A TEAE is defined as an event that first occurred or worsened in severity after baseline. The MedDRA Lowest Level Term (LLT) will be used in the treatment-emergent derivation. The maximum severity for each LLT during the baseline period including ongoing medical history will be used as baseline severity. For events with a missing severity during the baseline period, it will be treated as ‘mild’ in severity for determining treatment-emergence. Events with a missing severity during the postbaseline period will be treated as severe and treatment-emergence will be determined by comparing to baseline severity.

The percentages of patients with TEAEs will be summarized by treatment using MedDRA PT nested within SOC. Statistical comparisons will be applied at both the SOC and PT levels. Events will be ordered by decreasing frequency within SOC. For events that are sex-specific, the denominator and computation of the percentage will include only patients from the given sex.

An overview of the number and percentage of patients who experienced a TEAE, serious adverse event (SAE), died due to an AE, discontinued from study treatment, or study due to an AE, relationship to study drug, and outcome of AE, will be summarized by treatment.

The percentages of patients with TEAEs, overall and common (common TEAEs occurred in $\geq 5\%$ of patients before rounding), will be summarized by treatment using MedDRA PT. Events will be ordered by decreasing frequency.

The percentages of patients with TEAEs by maximum severity will be summarized by treatment using MedDRA PT. For each patient and TEAE, the maximum severity for the MedDRA PT is the maximum postbaseline severity observed from all associated LLTs mapping to the MedDRA PT. The maximum severity will be determined based on the non-missing severities. If all

severities are missing for the defined postbaseline period of interest, it will show as missing in the table. Only counts and percentages will be included for the TEAEs by maximum severity.

Patient narratives will be provided for all patients who experience any of the following “notable” events:

- Death
- SAE
- Permanent discontinuations of study or study treatment due to AE
- Pregnancy
- Adjudication Confirmed Major Adverse Cardiovascular Events
- Adjudication Confirmed Pancreatitis

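### Protocol 9.2 ties one trigger for following an AE to its conclusion to stopping tirzepatide only, so the follow-up duty differs by arm for a small class of non-serious glargine AEs

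*Protocol*

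**What the plan says.** Protocol 9.2 gives alternative triggers for following an AE until it has resolved, stabilized or been explained. The first ones cover "AEs that are serious or otherwise medically important, considered related to the investigational product or the study, or that" (the sentence then continues to the last trigger), which is that the AE "caused the patient to discontinue the investigational product (tirzepatide) before completing the study".

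Other places that bear on how to read the bracket:

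- Appendix 1 defines investigational product as "A pharmaceutical form of an active ingredient or placebo being tested or used as a reference in a clinical trial".
- Later in Protocol 9.2, the reporting rule carries no bracket: where "investigational product is discontinued as a result of an AE, study site personnel must report this to Lilly or its designee via eCRF".
- Protocol 9.2 also sets a recording rule for all arms: "For each AE, the onset and duration, the seriousness and severity, and the actions taken with respect to study treatment will be recorded".
- Protocol Section 4 lists early discontinuation of study drug due to AEs as a safety endpoint for each tirzepatide dose against glargine. SAP 6.13.1.4 analyzes it in the same terms.
- SAP 6.13.1 plans an overview in which patients who "discontinued from study treatment, or study due to an AE, relationship to study drug, and outcome of AE, will be summarized by treatment".

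**The concern.** The trial is open-label, with three tirzepatide arms and one glargine arm. A safety rule that obliges the site to pursue an event in three arms but not in the fourth can make the resulting data unequally complete for reasons unrelated to the drugs. On its face the bracket does this: a non-serious AE that ends tirzepatide treatment must be pursued to a conclusion, while the same event ending glargine treatment need not be, unless another trigger applies. AE outcome is tabulated by treatment, so a difference in the share left unresolved could partly reflect the follow-up rule. An outcome that was never pursued cannot be recovered in the analysis.

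**Working it through.** No arithmetic applies. The check is a comparison of texts.

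**1. Is the bracket the protocol's general meaning of the term?** No. Appendix 1 takes in a reference product. Protocol 10.3.3.1 uses investigational product for every arm when it describes the full analysis set and the retrieved dropouts. The per-protocol definition in Protocol Table GPHO.6 refers to permanent discontinuation of IP, and SAP Table GPHO.6.1 restates this as study drug. The text closest to a narrow meaning is Protocol 7.1.2, which calls the tirzepatide pen investigational and the glargine pen marketed, but that describes device status. The bracket in 9.2 is therefore an isolated inconsistency, though it sits in an operative rule.

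**2. Which glargine AEs does it leave out?** Take an AE that makes a glargine patient stop drug and apply each trigger:

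| The AE is | Followed to a conclusion? |
|---|---|
| Serious | Yes, any arm |
| Otherwise medically important | Yes, any arm |
| Related to the study | Yes, any arm |
| Related to the investigational product | Yes for glargine, under the Appendix 1 definition |
| None of these, but the reason for stopping drug | Tirzepatide yes; glargine no, read literally |

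Only the last row differs by arm.

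**3. Does another rule close the gap?** Largely, but not wholly. Protocol 8.1.1 keeps patients who stop study drug in the trial for all planned measurements, and Protocol 8.2 says stopping drug for an AE is not a valid reason to leave the study. The Schedule of Activities assesses AEs at every visit through Visit 801 in all arms. An event that resolves during the study should therefore be captured in either arm. For follow-up to a conclusion, however, 8.1.1 refers back to 9.2, and 9.2.1 does not oblige investigators to seek AEs actively once a patient has left the study. What remains are events still open around the last visits.

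**4. Which outputs depend on this?** The count of AE discontinuations and the time to discontinuation need the stop date and the cause, which are recorded for every arm. Following the event afterwards changes neither. AE outcome does depend on follow-up, and SAP 6.13.1 summarizes it by treatment with no test specified for it. SAP 6.2 also excludes patient data dated after the last date of study participation, so follow-up beyond Visit 801 may not reach the tables at all. That narrows the effect on the analysis further.

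**The case against.** The strongest reply is that this is a slip of one word. The trigger is one of several, the Appendix 1 definition would override the bracket for a careful reader, and glargine patients who stop drug stay in the study with AEs reviewed at every visit. Events likely to end glargine treatment, such as hypoglycemia or injection-site reactions, would often be judged related and so be followed anyway. They also have their own eCRF pages (Protocol 9.2.2.1 and 9.2.2.7.1). AE outcome is not a listed safety objective. All of this stands, and it limits the point to a minor one. It does not remove the point, because no other rule gives glargine the same explicit duty and a site reading 9.2 as written could apply it by arm.

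A reader might also infer something stronger: that the bracket redefines the term throughout 9.2 and 9.2.1, so that reporting of AE discontinuations and the start of SAE reporting never reach the glargine arm. The text does not support this. The discontinuation-reporting sentence has no bracket. Nor does the SAE sentence: "The SAE reporting to the sponsor begins after the patient has signed the ICF and has received investigational product". Appendix 1 brings a reference product within both. Protocol 9.2.1 requires all AEs after consent to be recorded and any SAE to be notified within 24 hours, and Protocol 9.2.2.1 makes severe hypoglycemia a reportable SAE with no limit by arm. Carrying the bracket back to the relatedness trigger in the same sentence fails for the same reason: that mention is unqualified, and Appendix 1 supplies its meaning.

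**Conclusion.** The inconsistency is real and minor. Read literally, Protocol 9.2 sets a different follow-up duty by arm for AEs that lead to stopping drug and are not serious, not otherwise medically important, and not related to the investigational product or the study. The realistic effect is less complete resolution and outcome data for those glargine AEs still unresolved at the last visits. AE recording, discontinuation counts, time to discontinuation and SAE reporting are intact.

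The size cannot be stated as a number, because the documents give no rate of AE discontinuations or of events in this class. The size of the glargine arm is not a measure of the effect, since few of its patients would be in the class. The conclusion assumes that sites apply the bracket as written and that the unbracketed uses of the term follow Appendix 1.

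**What to change.** In the follow-up sentence of Protocol 9.2, replace the words investigational product (tirzepatide) with *study drug (tirzepatide or insulin glargine)*. The duty is then the same in all four arms and matches the safety endpoint and SAP 6.13.1.4. No change to the SAP is needed. The cost is a wording change to the protocol, plus slightly more AE follow-up in the glargine arm.
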